Subjects are excluded from FAS analysis in case of these PDs:		Exclude subject from FAS, FAS1 and FAS2 analysis set
OTH20	Site has been closed down for GCP reasons	Yes
Subjects are excluded from SAF analysis in case of these PDs:		Exclude subject from SAF, SAF1 and SAF2 analysis set
OTH20	Site has been closed down for GCP reasons	Yes

If updates to this table are needed, an amendment to the SAP needs to be implemented prior to DBL.

6 Statistical methods for Pharmacokinetic (PK) parameters

All subjects within the PK set (up to Day 90) and PK2 only, will be included in the PK data analysis.

6.1 Variables

The following pharmacokinetic parameters of LNP023 will be determined using the actual recorded sampling times and non-compartmental method(s) with Phoenix WinNonlin (Version 6.4 or higher):

- Plasma
 - C_{max}, T_{max}, AUC_{last}, AUC_{tau} and C_{min} at Day 30.
 - C_{trough} samples at Day 8, 15, 60, 90 (plus Day 135 and Day 180 for PK2 set))
 - Other pharmacokinetic parameters may be calculated as appropriate.
- Urine
 - Non-compartmental parameters, including but not limited to total cumulative urinary excretion (A_e) and renal plasma clearance (CL_r) at Day 30 and Day 90

(+/- 1 day) for PK (up to Day 90) and PK2 sets. Day 180 (for PK2 set only) may be also used.

6.2 Descriptive analyses

LNP023 plasma concentration data will be listed by treatment, subject and visit/sampling time point. Descriptive statistics will be provided by treatment and visit/sampling time point, for the PK set (up to Day 90) and for PK2 separately, including the frequency (n, %) of concentrations below the Lower Limit of Quantification (LLOQ) which will be reported as zero; these will be distinguished from values missing. Summary statistics will include mean (arithmetic and geometric), Standard Deviation (SD), Coefficient of Variation (CV) (arithmetic and geometric), median, minimum, and maximum. Since Tmax is generally evaluated by a nonparametric method, only median, minimum, and maximum will be reported. Concentrations below LLOQ or missing will be treated as zero in summary statistics and for PK parameter calculations. A geometric mean will not be reported if the dataset includes zero values as well as for Tmax.

Pharmacokinetic parameters will be listed by treatment, visit/sampling time point, and subject and summarized by treatment, for the PK set (up to Day 90) and for PK2 separately, with descriptive statistics as described above. Concentrations below the lower limit of quantification (LLOQ) or missing will be indicated in the data listings.

Graphical methods will be employed to show mean (SD) and individual concentration-time profiles (in linear and log-linear scale) for PK set (up to Day 90) and PK2 set separately.

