RAAS	renin-angiotensin-aldosteron-system
RBC	red blood cell(s)

RNA	Ribonuclein acid
SAD	single-ascending dose
SAE	Serious adverse event
sCR	serum creatinine
SD	standard deviation
SGOT	serum glutamic oxaloacetic transaminase
SGPT	serum glutamic pyruvic transaminase
SOM	Site Operations Manual
SUSAR	Suspected unexpected serious adverse reactions
TBL	total bilirubin
TDI	time dependent inhibition
TID	ter in die (three times a day)
TSH	Thyroid stimulating hormone
UA	Urine Albumin
UACR	Urine Albumin to Creatinine Ratio
UI	Unblinded (individual)
UG	Unblinded (group)
UP	Urine Protein
UPCR	Urine Protein to Creatinine Ratio
ULN	upper limit of normal
ULoQ	upper limit of quantification
WBC	white blood cell(s)
WoC	Withdrawal of Consent
WOCBP	Women of child bearing potential

Pharmacokinetic definitions and symbols

Ae0-t	Amount of drug (or defined metabolite) excreted into the urine from time zero to time 't' where t is a defined time point after administration [mass units or % of dose]
AUC0-t	The area under the plasma (or serum or blood) concentration-time curve from time zero to time 't' where t is a defined time point after administration [mass x time / volume]
AUCinf	The area under the plasma (or serum or blood) concentration-time curve from time zero to infinity [mass x time / volume]
AUClast	The area under the plasma (or serum or blood) concentration-time curve from time zero to the time of the last quantifiable concentration [mass x time / volume]
AUCtau	The area under the plasma (or serum or blood) concentration-time curve from time zero to the end of the dosing interval tau [mass x time / volume]
AUCtau,ss	The area under the plasma (or serum or blood) concentration-time curve from time zero to the end of the dosing interval tau at steady state [mass x time / volume]
Cav,ss	The average steady state plasma (or serum or blood) concentration during multiple dosing
CL	The systemic (or total body) clearance from plasma (or serum or blood) following intravenous administration [volume / time]
CLr	The renal clearance from plasma (or serum or blood) [volume / time]
Cmax	The observed maximum plasma (or serum or blood) concentration following drug administration [mass / volume]
Cmax,ss	The observed maximum plasma (or serum or blood) concentration following drug administration at steady state [mass / volume]
Cmin,ss	The lowest plasma (or serum or blood) concentration observed during a dosing interval at steady state [mass / volume]
Racc	The accumulation ratio

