8.7 Pharmacokinetics

PK samples will be collected at the time points defined in the [Assessment schedule](#).

The pre-dose PK samples will be obtained and evaluated in all patients at all dose levels.

The post-dose PK samples at Visit 140 (Day 30) will be obtained and evaluated as follows:

- All the patients randomized in Part 1
- At least 48 patients randomized in Part 2
- Fulfill the local regulatory guidelines or considerations

LNP023 in plasma (0-8 h) and in urine (from a 24h collection) will be determined by a validated LC-MS/MS method. The lower limit of quantification (LLOQ) will be approximately 1 ng/mL. Concentrations below the LLOQ will be reported as “zero” and missing data will be labeled as such in the Bioanalytical Data Report.

For standard pharmacokinetic abbreviations and definitions see the list provided at the beginning of this protocol.

The following pharmacokinetic parameters of LNP023 will be determined using the actual recorded sampling times and non-compartmental method(s) with Phoenix WinNonlin (Version 6.4 or higher):

Plasma: $C_{max,ss}$, $T_{max,ss}$, $AUC_{tau,ss}$ and $C_{min,ss}$ at Day 30. Other pharmacokinetic parameters are measured as appropriate. To denote parameters determined at steady state “ss” will be used.

[figure not shown]
The linear trapezoidal rule will be used for AUC calculation. AUC_{tau} will be calculated instead of AUC_{inf} . Values below the lower limit of quantification will be treated as zero for calculation of PK parameters as well as for summary statistics.

[figure not shown]
Further details on sample collection, numbering, processing and shipment will be provided in the lab manual and/or SOM.

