11.5.3 Pharmacokinetics

LNP023 concentration data will be listed by treatment, patient and time point. Descriptive summary statistics will be provided by treatment and time point, for the PK set (up to Day 90) and for PK2 separately, including the frequency (n, %) of concentrations below the LLOQ and reported as zero; these will be distinguished from values missing.

[figure not shown]
Summary statistics will include mean (arithmetic and geometric), SD, CV (arithmetic and geometric), median, minimum and maximum. An exception to this is Tmax where median, minimum and maximum will be presented. Concentrations below LLOQ or missing will be treated as zero in summary statistics and for PK parameter calculations. A geometric mean will not be reported if the dataset includes zero values.

[figure not shown]
Pharmacokinetic parameters will be calculated as described in [Section 8.7](#) and will be summarized by treatment, for the PK set (up to Day 90) and for PK2 separately.

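### SAP 6.2 and Protocol 11.5.3 count missing plasma concentrations as zero, although both sections separate missing from below-LLOQ values and Protocol 8.7 zeroes only the latter

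*SAP*

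**What the plan says.** SAP 6.2 and Protocol 11.5.3 contain the same rule: "Concentrations below LLOQ or missing will be treated as zero in summary statistics and for PK parameter calculations". Earlier in each section, concentrations below the LLOQ are to be counted and reported as zero, with the addition that "these will be distinguished from values missing". SAP 6.2 further says that concentrations below the LLOQ "or missing will be indicated in the data listings", and it restricts one summary: "A geometric mean will not be reported if the dataset includes zero values".

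Protocol 11.5.3 then refers elsewhere for the parameters: "Pharmacokinetic parameters will be calculated as described in" Section 8.7. The rule there is narrower: "Values below the lower limit of quantification will be treated as zero for calculation of PK parameters as well as for summary statistics". The public text of 8.7 mentions missing data only to say that they are labelled as missing in the bioanalytical report. It gives no value for them.

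**The concern.** A below-LLOQ result is a measurement, and zero is a conventional stand-in for it. A missing result carries no information about the concentration. If the patient is still taking the drug twice daily, zero is the one value that can be ruled out in practice.

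Such gaps are foreseeable. Protocol 8.1 says that missed visits do not by themselves end participation. SAP 11 records that the pandemic prevented some procedures. SAP 6.1 uses trough samples at Days 8, 15, 60 and 90, plus Days 135 and 180 for PK2.

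Pharmacokinetics is a stated secondary objective, and PK parameter summaries are an IA2 output (SAP 3). At stake are the concentration and trough summaries, the individual parameters, and the power model in SAP 6.3, which uses log Cmax and log AUClast.

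**Working it through.** The plan states no figure that depends on this rule, so there is nothing to reproduce. The consequences follow by arithmetic.

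**Arm sizes.** Part 1 plans 14 placebo, 10 at 10 mg, 10 at 50 mg and 14 at 200 mg (Protocol 3.1). Part 2 plans about 50 patients, with roughly equal allocation over five arms across both parts. That gives (48 + 50)/5 = 19.6 per arm pooled. By subtraction, Part 2 has about 5.6 at 200 mg, 9.6 at 10 mg and at 50 mg, and 19.6 at 100 mg. I use n = 6, 10 and 20.

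**Mean and CV at one time point.** With a fraction p of values set to zero, the mean becomes (1 - p) times the observed mean. The CV becomes sqrt((1 - p)(1 + CV²) - (1 - p)²)/(1 - p). The documents give no between-patient CV, so 30% to 50% is assumed.

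| n, one missing | Mean | CV 30% becomes | CV 40% becomes | CV 50% becomes |
|---|---|---|---|---|
| 6 | -17% | 56% | 63% | 71% |
| 10 | -10% | 46% | 54% | 62% |
| 20 | -5% | 38% | 47% | 56% |

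**Geometric mean.** One zero is enough to suppress it. With an assumed missing rate q, the chance is 1 - (1 - q)^n:

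| q | n = 6 | n = 10 | n = 20 |
|---|---|---|---|
| 2% | 11% | 18% | 33% |
| 5% | 26% | 40% | 64% |
| 10% | 47% | 65% | 88% |

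**AUClast when one Day 30 sample is lost.** The grid is 0, 0.25, 0.5, 1, 2, 4, 6 and 8 h (Protocol Tables 8-1 and 8-2), with the linear trapezoidal rule (Protocol 8.7). Assumed: a one-compartment steady-state profile with a 12 h interval, nominal times, ka of 1, 2 or 4 per hour, and a half-life of 12 h (Protocol 6.9) or 20 h (Protocol 1.3.2).

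Zeroing interior sample i removes C_i(t_{i+1} - t_{i-1})/2. With ka 2 and half-life 20 h, C(2) = 2.772, C(4) = 2.603, C(6) = 2.429 and AUC0-8 = 20.349. Zeroing 4 h loses 2 × 2.603/20.349 = 25.6%. Omitting it replaces (2.772 + 2.603) + (2.603 + 2.429) = 10.407 by 2 × (2.772 + 2.429) = 10.402, a change of 0.0% of the AUC. Over all six settings:

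| Sample lost | Set to zero | Omitted |
|---|---|---|
| 0.25 h | -2.5 to -3.2% | -0.4 to 0.0% |
| 0.5 h | -4.3 to -5.4% | -0.3 to -0.1% |
| 1 h | -9.5 to -11.2% | -0.7 to -0.3% |
| 2 h | -20.1 to -21.5% | -1.4 to -0.1% |
| 4 h | -25.3 to -26.7% | -0.7 to +0.2% |
| 6 h | -22.6 to -24.5% | 0.0 to +0.2% |

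The end samples behave differently. With pre-dose lost, zeroing gives -1.0 to -1.2% and omission -2.3 to -2.8%. With 8 h lost, both give -21.3 to -23.7%, because the Protocol defines AUClast as running "from time zero to the time of the last quantifiable concentration", which is then 6 h.

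**Other parameters.** For a single lost sample, Cmax is the same whether it is zeroed or omitted. If the whole Day 30 profile is missing, the literal rule gives Cmax = AUC = 0, and ln(0) is undefined in the SAP 6.3 model. Cmin becomes 0 if an imputed zero counts, although the Protocol defines Cmin,ss as the lowest "concentration observed during a dosing interval at steady state". AUCtau depends on how 8 to 12 h is obtained, which the visible text does not state. With pre-dose zeroed, the loss is 12.5 to 14.8% if the 12 h value is set equal to pre-dose, but only 0.7 to 0.9% with extrapolation along the terminal slope.

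**The case against.** The best defence is that this is template wording. PK software normally leaves blanks missing, the bioanalytical report labels them, and the listings will show them. That may describe what will happen. But the sentence names both summaries and parameter calculations, and labels in a listing do not take zeros out of a mean. If the programmers leave blanks missing, the output departs from the SAP.

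Several narrower objections stand and limit the point:

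- A missed visit loses the whole Day 30 profile, not one sample. The AUClast table therefore applies only to a sample lost from an attended visit. A sample never drawn also has no actual time at which to place a zero, so that table rests on nominal times.
- Besides one valid concentration, the PK set in SAP 5 requires no deviation with relevant impact on PK. Table 5-1 lists only site closure for this, so under that table a missed sample does not by itself exclude the patient.
- For AUClast, omission is no better than zero when an end sample is lost.
- Any size quoted for AUCtau rests on an unstated method.

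A reader might go further and infer that the primary result, the choice of the 100 mg arm or the dose-proportionality conclusion is compromised. The documents do not support that. The primary analysis models 24-hour UPCR and uses no concentrations. The dose-selection guideline in Protocol 3.5 rests on the UPCR dose-response. Whether the dose-proportionality conclusion would change depends on a missing rate that is not given. Nor can one infer that only descriptive tables are touched, since SAP 6.3 uses AUClast and Cmax.

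**Conclusion.** The sentence is wrong as written and conflicts with Protocol 8.7, to which Protocol 11.5.3 itself refers. Severity is minor.

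The effects on the mean (1/n per missed sample) and the loss of the geometric mean follow directly from the rule. The CV figures assume a true CV, and the AUClast figures assume the profile described above. No overall size can be given without a PK missing rate. The power model is exposed through lowered AUClast values and through zero parameters that cannot be logged. AUCtau and Cmin are exposed too, but I put no size on AUCtau.

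The conclusion is limited to samples missed by patients still on treatment. It makes no claim about samples due after treatment has stopped, about the primary UPCR analysis, or about exposure-response modelling, for which SAP 9 refers to a separate plan.

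**What to change.** In SAP 6.2 and Protocol 11.5.3, delete the words 'or missing' from the sentence on zeros, so that only below-LLOQ values are set to zero, as in Protocol 8.7. Then add:

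*Missing concentrations are excluded from summary statistics (n reported) and from the non-compartmental calculation; interior gaps are bridged by the linear trapezoidal rule at actual sampling times; a parameter is set to missing only if it cannot be calculated by the stated method without the missing sample.*

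The last clause deliberately names no sample. If the 12 h value is taken as equal to pre-dose, for example, AUCtau can still be calculated without the 8 h sample: bridging 6 to 12 h errs by only 0.1 to 0.3% in the illustrative profiles.

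The cost is two words removed and one sentence added in the SAP. The matching Protocol wording can go with the next amendment. Some summaries will rest on slightly fewer values, which the reported n makes visible.

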6.3 Statistical model, assumptions and hypotheses

Dose proportionality/linearity

Dose proportionality assessment will be conducted for PK parameters such as Cmax and AUClast, for PK set (up to Day 90) and PK2 set separately.

PK parameters will be log transformed and analyzed using a power model:

$$\ln(\text{PK parameter}) = \mu + \beta \times \ln(\text{Dose})$$

The estimate of the slope β and the associated two-sided 90% confidence interval (CI) will be obtained based on the log-transformed observations, then “back-transformed” and presented on the original scale. Model goodness-of-fit will be explored by visually examining residuals. In case of evidence of lack-of-fit, alternative models will be explored, such as an ANOVA with dose as a classification factor.

PK dose proportionality will be concluded across the whole dose range if the 90% CI (β_L , β_U) for the slope β is completely contained within a pre-specified critical region (b_L , b_U), where the two limits b_L , b_U are derived as follows:

$$b_L = 1 + \ln(\theta_L)/\ln(r) \quad \text{and} \quad b_U = 1 + \ln(\theta_U)/\ln(r),$$

with r =ratio of highest to lowest dose studied (highest dose/lowest dose), $\theta_L=0.8$, $\theta_U=1.25$ being the standard bioequivalence limits.

7 Statistical methods for Efficacy/Pharmacodynamic (PD) parameters

All subjects within the FAS (up to Day 90) will be included in all efficacy analysis as well as the following data analysis, unless otherwise stated. At the time of the IA2, all data from Part 1 and Part 2 of the study up to day 90 will be pooled and analyzed for the primary analysis.

Efficacy analyses performed at IA2 up to study Day 90 for the following primary and secondary endpoints: UPCR obtained from 24h urine (primary endpoint), Estimated glomerular filtration rate, Serum creatinine, 24h-UP, 24h-UA, UACR, UPCR from first morning void will be considered final. It is not planned to rerun them at the time of the final DBL. However, discrepancies in data between the IA2 and final DBL will be assessed, and if considered of impact, the respective efficacy analysis may be re-run on the final data representing a sensitivity analysis to that performed at the IA2. All discrepancies on these endpoints will be provided as listing.

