3.3 Rationale for dose/regimen, route of administration and duration of treatment

PK profiles in human obtained for LNP023 after b.i.d. dosing from 10 - 200 mg revealed a non-linear dose-exposure relationship with increases in AUC_{tau} of <1.5 in response of an escalation factor of 2. The current assumption is that for full efficacy greater than 80-90% inhibition of alternative complement pathway is required at C_{trough}. Based on the readout from biomarkers (Wieslab, AP assay and Bb) indicating target occupancy or inhibition of alternative pathway, the anticipated human efficacious dose ranges between approximately 10 mg b.i.d. and 100 mg b.i.d. for a 60 kg individual. This would advocate evaluating doses that would: (i) clearly indicate target occupancy (25 mg b.i.d.); (ii) provide maximal exposure in terms of AUC and coverage at C_{trough} (200 mg b.i.d.).

The currently suggested plan includes a broad dose range of 10 mg (b.i.d), 50 mg (b.i.d) and 200 mg (b.i.d.) as different biomarkers (see above) indicated full efficacy at very different dose levels and the under-proportional dose-exposure relation observed for LNP023 requires administration of fairly different doses to achieve a significant and wide enough exposure range to clearly correlate human exposures with the respective clinical outcome.

Further, the maximal suggested dose of 200 mg b.i.d. is expected to exceed the current NOAEL of the most sensitive species (dogs) in 13-weeks GLP studies with total drug concentration based safety margins of 0.7 (AUC based) and 1.1 (C_{max} based). The exposure at 200 mg b.i.d will stay 2.9-fold below the exposure at which minimal testicular effects were observed in the 13-weeks dog study (LOAEL).

Safety margins based on unbound drug lead to a calculated ratio of 2.2 (AUC and C_{max} based) for the more sensitive species (dog) for the NOAEL.

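### SAP 6.3 back-transforms the dose-proportionality slope β and its 90% CI, although β is already a unitless exponent, so the presented values are not on the scale of the section's own critical region

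*SAP*

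**What the plan says.** SAP 6.3 states that "PK parameters will be log transformed and analyzed using a power model", with ln(PK parameter) equal to μ plus β times ln(Dose). Cmax and AUClast are given as example parameters, and the analysis is run on the PK set (up to Day 90) and on PK2 separately. The next sentence reads "The estimate of the slope β and the associated two-sided 90% confidence interval (CI) will be obtained based on the" and continues "log-transformed observations, then “back-transformed” and presented on the original scale". Its grammatical subject is β and its CI, not the fitted exposures.

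The decision rule follows: "PK dose proportionality will be concluded across the whole dose range if the 90% CI" for the slope β "is completely contained within a pre-specified critical region". The limits are b_L = 1 + ln(θ_L)/ln(r) and b_U = 1 + ln(θ_U)/ln(r). Here θ_L = 0.8 and θ_U = 1.25, described as "being the standard bioequivalence limits", and r is the highest dose divided by the lowest. The section gives no numerical values for the limits.

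SAP 4 says that log means the natural log throughout. Protocol 3.3 describes earlier human data in which AUCtau increased by a factor "of <1.5 in response of an escalation factor of 2".

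**The concern.** Back-transformation is right for a quantity estimated on a log scale, such as a mean log exposure or a difference of mean logs. The slope of a log-log regression is not such a quantity. It is the exponent in PK = exp(μ) × Dose^β, and it is the same number whichever scale the exposures are shown on. Proportionality is β = 1, and the critical region is built around that value.

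One paragraph therefore asks for β and its CI to be presented on one scale, and the next judges β on another. No limits are given for the presented scale. At stake is a readable slope table. Someone who knows that 1 means proportional would see an under-proportional slope displayed as a number above 1 and could take it as more than proportional.

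**Working it through.** The SAP gives formulas for the limits but no figure to reproduce, so the check is direct algebra.

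**Inputs**
- Model, limits and θ values: SAP 6.3.
- Log base e: SAP 4.
- Active doses 10, 50, 100 and 200 mg b.i.d.: SAP 1.4, Scenario 1. Hence r = 200/10 = 20. Part 2 contains both the 10 mg and the 200 mg group, so r is the same for PK2.
- AUCtau rise of less than 1.5-fold per doubling of dose: Protocol 3.3.

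**Critical region for β**
- b_L = 1 + ln(0.8)/ln(20) = 0.9255
- b_U = 1 + ln(1.25)/ln(20) = 1.0745

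**Slope implied by Protocol 3.3**
- β < ln(1.5)/ln(2) = 0.585. This is an illustration: the protocol figure is for AUCtau, whereas SAP 6.3 names Cmax and AUClast as examples.

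**What would be presented under exp(β)**

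| AUC fold-change per doubling | β | exp(β) |
|---|---|---|
| 1.1 | 0.138 | 1.147 |
| 1.25 | 0.322 | 1.380 |
| 1.5 (bound in Protocol 3.3) | 0.585 | 1.79 |
| 2 (exact proportionality) | 1 | 2.72 |

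Every β between 0 and 1 is displayed as a value between 1 and 2.72. On the exponentiated scale the matching limits would be exp(0.9255) = 2.523 and exp(1.0745) = 2.928, which the SAP does not state.

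**When the decision would change**

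Suppose the presented CI were wrongly compared with (0.9255, 1.0745). It would lie inside only if the CI for β lay between ln(0.9255) = -0.077 and ln(1.0745) = 0.072, that is, with exposure almost flat across doses. So the misapplied rule gives a wrong answer in two situations:
- The CI for β is inside (0.9255, 1.0745), so exposure is proportional. The presented CI is then inside (2.523, 2.928), and proportionality is wrongly not concluded.
- The CI for β is inside (-0.077, 0.072), so exposure is almost flat. Proportionality is then wrongly concluded.

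At β = 0.585 neither applies: 0.585 is below 0.9255 and 1.79 is above 1.0745, so on either scale proportionality is not concluded.

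**Other possible meanings of back-transformation**
- 2^β: β = 0.585 is shown as 1.5 and β = 1 as 2.
- r^(β−1): β = 0.585 is shown as 20^(−0.415) = 0.288 and β = 1 as 1. The matching limits would be 0.8 and 1.25.

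Neither function is defined in the SAP, and neither puts the result on the scale of (b_L, b_U).

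**The case against.** The strongest reply is that the rule is right as written. It refers to the 90% CI for the slope β, and the limits are the correct ones for the untransformed slope, so a programmer who follows it literally reaches the right conclusion. This stands. A reader might infer that the SAP will produce a wrong proportionality decision. The documents do not support that. It would require substituting the presented CI for the one the rule names, and exposure would also have to be truly proportional or almost flat. Protocol 1.3.2 and 3.3 describe exposure that is under-proportional to dose.

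A reader might also infer that dose spacing or dose choice is at risk. The documents do not support that either. The wide spacing in Protocol 3.3 rests on earlier human data. The added dose was to be guided by the UPCR contrast tests (SAP 3), and the DMC has already chosen 100 mg. The exposure-response work is separate pharmacometric modelling (Protocol 11.5.4, SAP 9). Dose proportionality is not itself a listed objective or endpoint, and the PK summaries by dose in SAP 6.2 would show under-proportional exposure directly.

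Finally, the SAP puts the term in quotation marks and names no function, so a displayed value above 1 is not certain: r^(β−1) would give a value below 1. This also stands. However, exp is the ordinary inverse of the natural log, and none of the alternatives makes the presented values comparable with the stated region.

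**Conclusion.** The point holds as a reporting error of low severity. Following the sentence in SAP 6.3 gives a slope and CI that are not on the scale of the section's own region of 0.926 to 1.074. Under exp(β), exact proportionality shows as 2.72 and the bound from Protocol 3.3 as 1.79. That β needs no back-transformation, and that exp(β) does not match the region, follows from the model alone. The displayed sizes assume that back-transformation means exp. The 1.79 further assumes that the AUCtau bound carries over to the parameters analysed.

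The decision rule is correct when applied to the untransformed CI. The primary analysis and dose selection are unaffected.

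**What to change.** In SAP 6.3, delete the back-transformation of β. Report β with its two-sided 90% CI untransformed, beside the numerical limits (0.926, 1.074 for r = 20). Keep back-transformation for fitted exposures at each dose only. As an optional addition, report 2^β with its 90% CI, labelled as the fold-change in exposure per doubling of dose. That is the form used in Protocol 3.3, and on that scale the limits are 2^0.9255 = 1.90 and 2^1.0745 = 2.11.

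The cost is one sentence in the SAP and a label in the table shell. No new data or further analysis is needed.
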